## Sample Size and Statistical Analysis

### Sample Size

Assuming a mean volumetric change at Day 3 compared to baseline of 3.56 for placebo group, and a mean volumetric change of 1.0 for arnica group (expected based on the PI's clinical expertise), a standard deviation of 2.56, statistical significance level of .05, and two-sided test, 25 subjects per group (50 total) will be needed to achieve 93% power (nQuery Advisor 7.0).

Up to thirty-five (35) subjects will be randomly assigned to each group. Recruitment will continue until up to seventy (70) subjects have qualified. This will allow for up to 29% dropout to end with a minimum of fifty (50) subjects completing the study.

### Statistical Analysis

Descriptive statistics (mean and standard deviations for continuous variables, medians and IQR for ordinal variables, counts and percentages for categorical variables) will be calculated for each variable and stratified by the two treatment groups.

For the primary outcome, the change in postoperative facial swelling as measured by the 3dMD™ system and the change in postoperative pain as measured by VAS, from baseline (pre-operative) to post-operative Day 3, and from baseline to post-operative Day 5, will be compared between the two groups using independent sample t-test if the data are normally distributed, or the Mann Whitney U test if non-parametric methods need to be utilized.

In addition, the volume measurements and the VAS scores will be analyzed using a repeated measures ANOVA accounting for time effect, treatment effect, and treatment by time interaction, adjusting for subject age and sex.

Number of rescue medication doses will be compared between the two treatment groups using Mann-Whitney U test.

P-values less than 0.05 will be considered statistically significant. Statistical analyses will be performed using SAS, Version 9.4 (SAS Institute, Cary, North Carolina).

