### 3dMD™

An initial 3dMD™ scan will be obtained for a preoperative baseline evaluation at the extraction visit. A second 3dMD™ scan will be obtained for evaluation and determination of facial swelling at the Day 3 follow-up visit. A third scan will be obtained at the Day 5 follow-up visit to evaluate the degree of resolution of swelling. The scans will result in a computer-generated image on which the investigator will outline the area of clinical interest and calculate the volume using integration. The

process of surface scanning and volume measurement will use the 3dMDvultus™ software. The 3dMDvultus™ software allows for superimposition of post-surgical images as well as quantitative evaluation of surface and volume changes. The Principal Investigator has worked on previous 3dMD™ studies and had additional training when the camera array was installed. The technique of obtaining the image is straight forward and there is a set of instructions at the installation site for immediate review as necessary.

The degree of facial swelling between the two groups at the two time points (Day 3 follow-up and Day 5 follow-up) will be compared using the data collected from 3dMD™. Furthermore, the change in volume between the two scans taken at the Day 3 follow-up visit and at the Day 5 follow-up visit within each group will also be compared. The volumetric difference between the two groups will be analyzed for any statistical significance.

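### The four primary comparisons are valid but use baseline only by subtraction, and the choice between t-test and Mann-Whitney has no stated criterion; both can be settled cheaply in the SAP

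*Combined protocol and SAP*

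**What the plan says.** The Statistical Analysis section defines the primary outcome through two measures, 3dMD facial swelling and VAS pain, each as change from the pre-operative value to Day 3 and to Day 5. That makes four comparisons. The changes "will be compared between the two groups using independent sample t-test if the data are normally distributed, or the Mann Whitney U test", the latter "if non-parametric methods need to be utilized". The section names no diagnostic, no threshold and no time for that decision, and does not say whether it is taken once or separately for each comparison.

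In addition, "the volume measurements and the VAS scores will be analyzed using a repeated measures ANOVA", with time, treatment and their interaction, "adjusting for subject age and sex". Baseline is not named as a covariate, and the text does not say whether it counts as one of the time levels.

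The Sample Size section uses Day 3 swelling only: mean changes of 3.56 (placebo) and 1.0 (arnica), "a standard deviation of 2.56", two-sided 0.05, and the conclusion that "25 subjects per group (50 total) will be needed to achieve 93% power".

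The 3dMD section says that the first scan "will be obtained for a preoperative baseline evaluation at the extraction visit" and that "the investigator will outline the area of clinical interest and calculate the volume using integration". It also says that the software can superimpose images and quantify the change directly.

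**The concern.** Two things are left on the table.

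- **Baseline.** A change score fixes the weight given to baseline at one. If baseline is correlated with the change, part of the residual variance is predictable and could be removed by a single covariate. The interval for the treatment difference is then wider than it needs to be. This matters more if the true effect is smaller than planned, and the Sample Size section bases the arnica mean on clinical expectation rather than data.
- **Choice of test.** With no written criterion, the primary test could be chosen once both results are known. The Randomization and Blinding sections place the master list with the Principal Investigator and give that person and the Research Coordinator access to the sealed chart numbers. This is not evidence of misuse, but it is a practical reason to fix the rule in advance.

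**Working it through.** **Inputs from the Sample Size section.** Difference 3.56 − 1.0 = 2.56; SD 2.56, read as the SD of the change; standardised difference 2.56/2.56 = 1.0; n = 25 per arm; two-sided alpha 0.05. Not in the documents: any baseline SD, and any correlation of baseline with follow-up or with change.

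**Step 1: reproduce the plan's figure.** Noncentrality = 2.56/(2.56 × √(2/25)) = 3.536, with 48 degrees of freedom. Power is 93.4%, which agrees with the stated 93%. With 35 completers per arm it is 98.5%. At half the planned difference (1.28) with 25 per arm it is 41.0%.

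**Step 2: add baseline as the only covariate.** Let g be the share of the variance of the change explained by baseline, i.e. the squared correlation of baseline with change. The residual SD is 2.56 × √(1 − g), the degrees of freedom are 2n − 3 = 47, and the variance of the adjusted difference carries a factor 1 + F/(2n − 2) for chance baseline imbalance, with F distributed as F(1, 2n − 2). Power is averaged over that factor. With 25 per arm:

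| g (assumed) | Power, difference 2.56 | Power, difference 1.28 | Mean 95% CI width |
|---|---|---|---|
| t-test on change | 93.4% | 41.0% | 2.90 |
| 0 | 92.9% | 40.3% | 2.93 |
| 0.05 | 94.0% | 42.0% | 2.85 |
| 0.10 | 95.1% | 43.9% | 2.78 |
| 0.25 | 97.7% | 50.8% | 2.54 |
| 0.50 | 99.8% | 67.8% | 2.07 |

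The covariate pays for itself once g exceeds about 0.023. With 35 completers per arm, power at the planned difference goes from 98.5% to 98.7, 99.1 or 99.7% at g = 0.05, 0.10 or 0.25, so little is left to gain there.

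**Step 3: what determines g.** Write k for baseline SD divided by follow-up SD and r for the baseline-to-follow-up correlation. Then g = (k − r)²/(1 + k² − 2rk).

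- Equal SDs (k = 1): g = (1 − r)/2, so r = 0.9, 0.8, 0.5 and 0 give 0.05, 0.10, 0.25 and 0.50.
- Change unrelated to baseline: then r = k and g = 0, whatever the value of r.
- Baseline SD small relative to follow-up, k = 0.1 to 0.2 with r = 0 to 0.3: g is at most 0.042.

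The documents do not say which case applies to either outcome.

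**Step 4: the open choice of test.** Null simulation, 25 per arm, 20,000 runs (Monte Carlo standard error about 0.15 points). The fixed rule is an assumed Shapiro-Wilk test at 5% in each arm, because the plan gives none.

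| Distribution | Fixed rule | Smaller of the two p-values |
|---|---|---|
| Normal | 5.2% | 6.0% |
| Lognormal | 4.7% | 6.5% |
| Exponential | 4.8% | 6.7% |

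**The case against.** The strongest reply is that nothing here is wrong. The planned tests are valid in a randomised comparison, power is already 93.4%, and adjustment is a preference. That stands, and it sets the level of this point.

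The second reply is that the gain may not exist. If larger baseline volumes do not swell more or less than smaller ones, g is zero and the covariate costs a little power. For swelling there may not even be a covariate. The integration wording in the 3dMD section suggests a volume for each scan, but the superimposition wording would fit a measure that exists only as a difference. Both parts stand, so the gain can only be stated conditionally.

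Three stronger readings are tempting and are not supported:

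- *Swelling gains and pain does not.* This follows only if equal SDs are assumed for swelling and a small baseline SD for VAS. With equal SDs and r from 0.5 down to 0, pain would reach 97.7 to 99.8% at a standardised difference of 1.0. No ordering of the two outcomes follows from the documents.
- *A baseline-to-follow-up correlation below some cut-off guarantees a gain.* It does not; as Step 3 shows, g can be zero at any correlation.
- *The planned switch inflates type I error.* A fixed rule does not. The 6 to 7% describes picking the smaller p-value, a worst case that the plan does not announce.

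**Conclusion.** The point holds as an optional, cheap efficiency improvement, not as an error. Baseline is used only by subtraction in all four primary comparisons, and the criterion for the rank test is missing.

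Adding baseline changes power at the planned effect from 93.4% to somewhere between 92.9% (unrelated to change) and 99.8% (half the variance explained). These figures assume that 2.56 is the SD of the change, 25 completers per arm, normal errors and assumed values of g. For pain they also assume a standardised difference of 1.0, since the plan gives no effect size for VAS. Leaving the choice of test open could take type I error to about 6 to 7% per comparison at worst.

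The four tests, each at 0.05, raise a separate multiplicity question that this point does not address.

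**What to change.** In the Statistical Analysis section:

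1. For each outcome and visit with a separate baseline value, make the primary analysis an ANCOVA of change on treatment and baseline value only. Report the adjusted mean difference with its 95% CI. Age and sex can stay in the repeated measures model.
2. In the 3dMD section, state whether the baseline scan yields its own volume. If swelling is measured only as a superimposition difference, leave it unadjusted.
3. If a rank-based route is kept, name one (for example rank ANCOVA on the same baseline) and one criterion (for example a Shapiro-Wilk threshold on blinded pooled residuals of change on baseline). Fix it before the code is broken, and state the effect measure that this route reports.

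**Cost.** SAP wording only; no new data. If baseline is uninformative, the price is one degree of freedom and about 0.5 points of power at the planned effect (93.4% to 92.9%) or 0.7 points at half of it (41.0% to 40.3%). The example criterion has its own small price in that case. In simulations with a shift of 0.7 SD, equal SDs and a baseline-to-follow-up correlation of 0.99, the revised route fell up to 2.1 points below an assumed per-arm Shapiro-Wilk rule (85.3% against 87.4% for t-distributed errors with 3 degrees of freedom). The linear and rank routes still report different effect measures, so the SAP must say which one is reported in each case.

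### Minor: the supplementary repeated measures ANOVA leaves its time levels and treatment comparison open and does not adjust for the pre-operative value; a baseline-adjusted mixed model with a named Day 3 contrast is a cheap improvement

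*Combined protocol and SAP*

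**What the plan says.** The Statistical Analysis section first sets out the primary comparison: change in swelling and in VAS pain "from baseline (pre-operative) to post-operative Day 3, and from baseline to post-operative Day 5", compared between arms by t-test or Mann-Whitney test. It then continues: "In addition, the volume measurements and the VAS scores will be analyzed", and the method is that these will be "analyzed using a repeated measures ANOVA accounting for time effect, treatment effect, and treatment by time interaction, adjusting for subject age and sex". Age and sex are the only covariates listed.

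The 3dMD™ section supplies the time points for volume. The first scan "will be obtained for a preoperative baseline evaluation at the extraction visit", and two more follow at Day 3 and Day 5. It also plans to compare, within each group, "the change in volume between the two scans taken at the Day 3 follow-up visit and at the Day 5 follow-up visit", and adds: "The volumetric difference between the two groups will be analyzed for any statistical significance".

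The Sample Size section rests on the Day 3 change only: "Assuming a mean volumetric change at Day 3 compared to baseline of 3.56 for placebo group", against 1.0 for arnica, SD 2.56, 25 per group, 93% power.

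**The concern.** The model names a treatment effect and an interaction with time, but three things needed to interpret them are missing: the response (raw value or change), the time levels (three including baseline, or two after surgery), and the term or contrast that answers the treatment question. Two readings fit the text.

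- **Raw-value reading:** three readings per subject, with baseline as a level. Leaving baseline out of the covariates is then no error, because it is part of the response. The treatment effect shows up in the interaction. The main effect averages in a reading taken before treatment could act.
- **Change reading:** change at Day 3 and at Day 5. Baseline is subtracted but not adjusted for. The main effect carries the treatment effect, and the interaction asks only whether the difference between arms alters from Day 3 to Day 5.

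At stake is a supplementary result whose treatment estimate is not fixed in advance and may be less precise than the collected data allow.

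**Working it through.** **Inputs from the plan (Sample Size):** Day 3 difference 3.56 − 1.0 = 2.56; SD 2.56, taken as the SD of the Day 3 change; n = 25 per arm; two-sided alpha 0.05.

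**Assumed, because the documents give no figure:** SD of the Day 5 change also 2.56; correlation ρ of the Day 3 and Day 5 changes 0.6; Day 5 difference δ5 of 1.28 or 2.56; baseline SD s of 2, 5 or 10; baseline-change correlation r as shown.

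**1. The plan's own figure.** Noncentrality = 2.56 / (2.56 × √(2/25)) = 3.536 on 48 df. Power is 93.4%, so the stated 93% reproduces.

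**2. Change reading.**
- Main effect: difference (2.56 + δ5)/2, SD 2.56 × √((1 + 0.6)/2) = 2.290. For δ5 = 1.28: 1.92 / (2.290 × 0.2828) = 2.965, power 83%. For δ5 = 2.56: 3.953, power 97%.
- Interaction: difference 2.56 − δ5, SD 2.56 × √(2 × 0.4) = 2.290. Power is 49% for δ5 = 1.28. For δ5 = 2.56 the difference is zero and the rejection rate is 5%.

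**3. Raw-value reading.**
- The interaction is a joint test of the two changes. Noncentrality = (n/2)(δ3² − 2ρδ3δ5 + δ5²) / (SD²(1 − ρ²)), where δ3 is the Day 3 difference. In SD units this is 12.5 × (1 − 0.6 + 0.25)/0.64 = 12.70, or 12.5 × (1 − 1.2 + 1)/0.64 = 15.63. With F on 2 and 47 df, power is 88% or 94%. It uses only the changes, so it is no more efficient than a change score.
- Main effect: the subject mean is baseline plus one third of the summed changes. Difference = (2.56 + δ5)/3; variance = s² + 2 × 2.56² × 1.6/9 + (4/3) × r × s × 2.56.

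| Baseline SD | r | Power, δ5 = 1.28 | Power, δ5 = 2.56 |
|---|---|---|---|
| 2 | 0 | 42% | 65% |
| 5 | 0 | 14% | 21% |
| 10 | 0 | 7% | 9% |
| 2 | −0.5 | 74% | 93% |
| 5 | −0.5 | 18% | 28% |
| 10 | −0.5 | 8% | 10% |

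With ρ from 0.4 to 0.8, the raw-value interaction has 88% to 94% (δ5 = 1.28) or 91% to 96% (δ5 = 2.56). The change-score main effect has 78% to 87% or 96% to 99%.

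**4. Adding the baseline covariate to the Day 3 change.** Residual SD = 2.56 × √(1 − r²); df = 50 − 5 = 45 (intercept, treatment, baseline, age, sex).

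| Size of r | Variance removed | Residual SD | Power |
|---|---|---|---|
| 0 | 0% | 2.56 | 93.3% |
| 0.3 | 9% | 2.44 | 95.2% |
| 0.5 | 25% | 2.22 | 97.9% |

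This ignores chance imbalance in the covariates. A simulation of 20,000 trials with age and sex in the model allows for it. Power without baseline is about 92%; with baseline it is 91.7%, 94.1% and 97.2%. The 95% CI half-width is 1.48 without baseline and 1.50, 1.43 and 1.30 with it.

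**5. Cross-check in another parameterisation.** With equal variances at baseline and Day 3 and correlation c between those two readings, the residual variance is (1 + c)/2 of the change-score variance. For c = 0.5, 0.7 and 0.9, power is 97.9%, 96.4% and 94.4%, against 93.4% unadjusted. The gain shrinks as the readings become more alike.

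**The case against.** The strongest reply is that the trial does not depend on this model. The primary analysis already compares change from baseline at Day 3 between arms, so a defined Day 3 contrast exists. The move from change in the primary paragraph to measurements and scores in the next sentence favours the raw-value reading, under which the missing covariate is no defect. A well-powered term exists under either reading, and the low powers belong to the term that does not carry the effect. All of this stands. It limits the point to a minor one but leaves the model undefined, and even the raw-value interaction gives up what baseline adjustment could add.

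A reader might also see a loss of subjects or dropout bias here, because the Sample Size section says "This will allow for up to 29% dropout to end with a minimum of fifty (50) subjects completing the study". The documents do not support that: nothing prescribes a complete-case fit, and the primary Day 3 t-test can use every subject seen at Day 3. No retention gain is therefore claimed.

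Two further objections shape the fix. The 3dMD™ section describes both integrating a volume over an outlined area and software that superimposes images to measure volume change. If volume exists only as a superimposed difference, its baseline is zero by construction and there is nothing to adjust for. That section also places the Day 3 to Day 5 comparison within each group; its next sentence, on a difference between groups, is not clearly tied to that change.

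**Conclusion.** The point holds as a minor improvement to the supplementary model. Which term is informative depends on a reading the plan does not settle, and baseline adjustment is a better use of values that the primary comparison already requires. The gain in Day 3 power runs from nil to about 5 points (93% to 98%) over assumed baseline-change correlations of 0 to 0.5. The plan gives no such correlation, and it gives no planning figures for VAS at all, where the gain may be nil.

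Two stronger conclusions might be inferred and should not be. The first is that the trial ignores baseline or is underpowered: the primary tests use change from baseline, and the 93% reproduces. The second is that testing two terms inflates the false-positive rate: the plan does not say that a positive result on either term counts as success.

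**What to change.** Replace the repeated measures ANOVA with a likelihood-based mixed model (SAS PROC MIXED, unstructured covariance) on change from baseline at Day 3 and Day 5, fitted separately for volume and VAS.

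- **Terms:** treatment, visit, treatment-by-visit, pre-operative value, age and sex.
- **Subjects:** all those randomized with at least one post-operative value, analysed as randomized.
- **Main result of this model:** the Day 3 treatment difference with its 95% CI, matching the sample-size endpoint; Day 5 is supporting. Naming one visit keeps the false-positive rate at 5%. Letting either visit count would give 8.9% in simulation (null, correlation 0.6).
- **Treatment-by-visit:** state that it estimates the between-arm difference in the Day 3 to Day 5 change, and say whether that comparison is intended.
- **Volume covariate:** use the pre-operative volume of the outlined region. If volume is obtained only as a superimposed difference, omit the covariate for volume and keep it for VAS.

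The cost is SAP wording. Visits, measurements, software and sample size stay as they are, provided a separate pre-operative volume is available. The downsides are a missing-at-random assumption that must be stated, and about half a point of power lost if baseline does not predict change (92.3% to 91.7% in the simulation). If the sponsor prefers to keep the ANOVA, stating its response, time levels and treatment contrast would still resolve the ambiguity.

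### Four comparisons are called primary at p<0.05 with no rule for which must succeed, while the stated alpha and 93% power describe Day 3 volume only

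*Combined protocol and SAP*

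**What the plan says.** The Statistical Analysis section speaks of the primary outcome in the singular but lists two variables under it: "the change in postoperative facial swelling as measured by the 3dMD™ system and the change in postoperative pain as measured by VAS". Each is assessed "from baseline (pre-operative) to post-operative Day 3, and from baseline to post-operative Day 5", by a t-test or, if the data are not normal, a Mann-Whitney U test. Two variables at two times make four between-group comparisons. The section's only decision criterion is "P-values less than 0.05 will be considered statistically significant".

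The Sample Size section works from one of the four: "Assuming a mean volumetric change at Day 3 compared to baseline of 3.56 for placebo group", against 1.0 on arnica, with an SD of 2.56 and a "statistical significance level of .05, and two-sided test". It concludes that "25 subjects per group (50 total) will be needed to achieve 93% power". It gives no assumptions for Day 5 volume or for VAS on either day.

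The 3dMD™ section uses the Day 3 scan to determine swelling, and says of the next one: "A third scan will be obtained at the Day 5 follow-up visit to evaluate the degree of resolution of swelling". It then compares the groups at both time points and adds: "The volumetric difference between the two groups will be analyzed for any statistical significance".

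The repeated measures ANOVA and the rescue-dose comparison are set apart from the four and are not part of this point.

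**The concern.** The text allows three readings of success: Day 3 volume decides, any one of the four is enough, or all four are required. Each has its own type I error and power, and the plan's figures belong only to the first. Suppose Day 5 pain gives p<0.05 and Day 3 volume does not. One analyst could report a positive primary result and another a negative one, both following the same text. Until the deciding comparison is named, neither the 5% error rate nor the 93% power can be quoted for the trial's primary conclusion. A rule chosen after the results are seen would not be credible.

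**Working it through.** **Inputs.** From Sample Size: means 3.56 and 1.0, SD 2.56, two-sided 0.05, 25 completers per group, up to 35 randomised per group. From Statistical Analysis: four comparisons, each at p<0.05. The documents give no correlation between days or between swelling and pain, and no effect size for pain or Day 5. Values used for these are assumptions.

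**1. The plan's own figure.** Standardised effect = (3.56 − 1.0)/2.56 = 1.0. For a two-sample t-test with n = 25 per group, df = 48 and noncentrality = 1.0 × √(25/2) = 3.54. Power from the noncentral t distribution is 93.4%, so the stated 93% reproduces. This is the operating characteristic when Day 3 volume alone decides.

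**2. Any one of four counts, no true effect.** For independent tests, the chance of at least one p<0.05 is 1 − 0.95⁴ = 1 − 0.8145 = 18.5%. The Bonferroni upper bound is 4 × 0.05 = 20%. Correlated endpoints lower the figure. Simulated t-tests on four multivariate normal endpoints, 25 per group, 100,000 null trials (Monte Carlo standard error about 0.1 point), gave:

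| Between-day correlation | Swelling–pain correlation | At least one p<0.05 |
|---|---|---|
| 0.5 | 0 | 17.7% |
| 0.5 | 0.5 | 15.6% |
| 0.8 | 0.5 | 13.7% |
| 0.9 | 0.5 | 12.6% |
| 0.9 | 0.9 | 9.4% |

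It returns to 5% only if the four comparisons are perfectly correlated.

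**3. All four required.** Type I error is not inflated. For power, give every comparison the Day 3 volume effect of 1.0 (an assumption):

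| Correlation | 25 per group | 35 per group |
|---|---|---|
| Independent | 0.9337⁴ = 76.0% | 0.9848⁴ = 94.1% |
| Common 0.5 | 82% | about 95% |
| Common 0.9 | 89% | about 97% |

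The 35-per-group column needs every randomised subject to complete. Joint power also cannot exceed that of the weakest comparison. If one of the four had a standardised effect of 0.5 (an assumption), its power with 25 per group would be 41.0%, and the joint power could be no higher.

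**4. Holm across the four.** The smallest step is 0.05/4 = 0.0125. Day 3 volume power at that level, which is its minimum under Holm, is 82.2% with 25 per group, 92.9% with 33, 93.7% with 34 and 94.4% with 35.

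**The case against.** The best defence is that Day 3 volume was always meant. The primary outcome is singular, only Day 3 volume is sized, and the 3dMD™ section treats Day 5 as a look at resolution. Its sentence about testing for significance may be generic wording and not a statement of what decides success. On that reading the alpha and power are right and the fault is loose drafting. This is a fair inference about intent. However, the analysis section expressly puts pain and Day 5 under the primary label, and the 3dMD™ section cannot settle the standing of pain.

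Part of the document was not available for this review and may name a primary endpoint. That should be checked, but the analysis section would still need to be brought into line with it.

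Three qualifications stand. Nowhere does the plan say that any one result is enough, so 9% to 18.5% is the error rate under that reading with assumed correlations, not a property of the trial as such. The all-four power loss largely disappears if nearly all 35 per group complete. And 93% is a t-test figure: the Mann-Whitney fallback has about 92% under normality with 25 per group.

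**Conclusion.** The concern holds and must be fixed. Four comparisons share the primary label at an unadjusted 0.05, no success rule appears in the sections available, and the sizing covers one of the four. The sample-size arithmetic is correct for Day 3 volume. What fails is its extension to the primary analysis as written: under the any-one reading the four tests do not have a 5% error rate as a family, and under the all-four reading 93% is not the power of the primary conclusion. How large the inflation is depends on correlations that the documents do not give. That it exceeds 5% under the any-one reading holds for anything short of perfect correlation.

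**What to change.** State the decision rule in the Statistical Analysis section before any outcome data are examined by group. Which endpoint decides is the sponsor's choice. The options are:

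- **Single primary (simplest).** Name the change in 3dMD volume from baseline to Day 3 as the one primary endpoint, two-sided 0.05. Make the other three secondary, either tested in a fixed, pre-stated order or reported without a primary claim. Cost: wording only, and 25 per group with 93% power stands. The downside is that pain and Day 5 lose the equal standing they now have.
- **Any of the four.** Use Holm, and restate Day 3 volume power as at least about 82% with 25 completers per group. Restoring 93% takes 34 completers per group, so almost no dropout from the planned 35.
- **All four required.** Say so, and give assumed effects and power for VAS and for Day 5. The present 93% cannot be carried over.

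Whichever is chosen, make the Sample Size, Statistical Analysis and 3dMD™ sections name the same deciding comparison.
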